8.1.2 Annualized relapse rates

Annualized relapse rate (ARR) is defined as the *number of relapses* experienced during a specific period of time adjusted to a one-year period. The ‘number of relapses’ can refer to

either the number of *confirmed relapses* or the number of *all relapses* (including both confirmed and unconfirmed relapses).

Confirmation of relapses is not collected in the following studies: CFTY720D2316, CFTY720D2320, CTY720D2399E1, and the long-term follow-up study prior to protocol amendment 4. Therefore, the number of confirmed relapses during this time is not able to be reported. Additionally, confirmed relapses will not be reported for patients from the CFTY720D2324 study since it is a phase IIIb study and confirmation is not collected in the long-term follow-up study for patients coming from previous studies that are not phase II/III. The number of unconfirmed relapses is also not able to be reported for study CTY720D2399E1 since the study does not collect relapse start dates. However, note that the time during which number of relapses is not able to be counted and the time off study for patients who re-enrolled into the long-term follow-up study will still be included in the time in study, which can make the ARR appear lower than it actually is. If confirmation of a relapse is missing or not collected, the relapse will be treated as an unconfirmed relapse. Therefore, ARR based on all relapses (confirmed or unconfirmed) should be considered a more reliable estimation of relapse rate than ARR based on confirmed relapse.

The group level (aggregate) ARR will be calculated as follows: (total number of relapses) / (total number of days in the study for all patients for that specific period of time) x 365.25.

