2.3.1 Database lock for Study part I

There are two database locks for this study. The analyses specified in this document include data from study part I with a database lock planned around 30th Jun 2017. All qualified patients will have end of study visit scheduled around 31st Oct 2016, which gives time for 6-month follow-up by end of Apr 2017. The 2nd data base lock is planned around 2018 for study part 2, in which patients from the long-term follow-up study are kept for another 2 years after finishing study part I. The analysis plan for study part II will be provided in a separate analysis plan.

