2.5.1 Subgroups

The following subgroups are defined for AE analysis:

1. Duration of fingolimod treatment up to the end of the long-term follow-up study part I (yearly interval):
 - Year 1 subgroup: patients on fingolimod treatment ≥ 0 year (≥ 1 day)
 - Year 2 subgroup: patients on fingolimod treatment ≥ 1 year (≥ 360 days)
 - Year 3 subgroup: patients on fingolimod treatment ≥ 2 year (≥ 720 days)
 - Year 4 subgroup: patients on fingolimod treatment ≥ 3 year (≥ 1080 days)
 - Year 5 subgroup: patients on fingolimod treatment ≥ 4 year (≥ 1440 days)
 - Year N subgroup: patients on fingolimod treatment $\geq N - 1$ year ($\geq (N - 1) \times 360$ days)
2. Patients from Phase II/III studies: This subgroup includes patients who have enrolled in any of the following studies: D2201, D2301, D2302, and D2309 before entering the long-term follow-up study part I.

3 Patient Disposition

All screen failures in the long-term follow-up study will be listed along with their primary reason for failing screening.

The number and percentage of patients who completed the long-term follow-up study part I, and who discontinued the long-term follow-up study part I, along with the primary reason for discontinuation, will be summarized for the enrolled set. The number and percentage of patients who are expected to have follow-up visits and who returned for 3-month and 6-month follow-up visits will also be summarized.

The patients who discontinued from the long-term follow-up study part I and corresponding reasons will be listed for the enrolled set. Additionally, a similar listing will be provided for the enrolled set of patients from D2312 and D2402 studies who discontinued early from the long-term follow-up study part I.

4 Protocol Deviations

The number and percentage of patients in the enrolled set with each protocol deviation in the long-term follow-up study part I will be displayed by protocol deviation category. Additionally, patients with at least one protocol deviation during the long-term follow-up study part I and patients with at least one protocol deviation causing exclusion from any analysis set (deviation severity codes 0, 5, or 8) will be summarized.

The protocol deviation data will be listed as well.

Additionally, the investigator comments during the long-term follow-up study part I will be listed.

5 Background and demographic characteristics

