8.1.3 Time in study

For the analysis of ARR from first dose of fingolimod to end of study treatment, the time in study (days) is calculated as: last dose date of fingolimod – first dose date of fingolimod among all studies + 1 day. Similarly, the time in study from first dose of fingolimod among all studies to end of follow-up is calculated as: last available visit/evaluation date across all panels – first dose date of fingolimod among all studies + 1 day.

For the analysis of ARR from first dose of fingolimod among all studies to end of a particular month (i.e. “Month 6”, “Month 12”, “Month 24”, and every 12 months from then on), “Month 0 to X” time in study will be calculated as minimum of (first dose date of fingolimod + integerpart(X/12*365.25) where X denotes the month, last available visit/evaluation date across all panels) – first dose date of fingolimod + 1 day.

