8.1.4 MS relapses analyses

MS relapses analyses will be conducted on the fingolimod full analysis set. All analyses will be done for all relapses (confirmed and unconfirmed) and for confirmed relapses.

A summary of ARRs will be presented by time period (cumulative time intervals: ‘Month 0 to Month 6’, ‘Month 0 to Month 12’, ‘Month 0 to Month 24’, ‘Month 0 to Month 36’, ... incremented by 1 year for each successive interval, plus ‘Month 0 to end of study treatment’ and ‘Month 0 to end of follow-up’) from first dose of fingolimod among all studies. The summary will include number of patients summarized, number of relapses, time in study (days), and group level ARR. In addition, model based estimates of ARR and corresponding two-sided 95% confidence interval will be obtained by fitting a negative binomial regression model adjusted for the number of relapses in the last two years prior to

enrolment in the core study and EDSS score at first dose of fingolimod baseline, with the logarithm of the time in study as the offset variable.

A summary of relapse characteristics will be displayed by time period (consecutive yearly intervals: 'Month 0 to Month 12', 'Month 12 to Month 24', etc., plus 'End of study treatment to End of follow-up') from first dose of fingolimod among all studies. Relapse characteristics will be summarized at a patient level (the number and percent of patients with at least one relapse type) and at a relapse event level (the number and percent of a particular type of relapse out of the total number of relapses). The types of relapses being summarized include: relapses which affect daily activities, relapses which require steroids, and relapses which require hospitalization.

The time to first onset of relapse from first dose date of fingolimod among all studies will be analysed. Specifically, the number of patients at risk, the cumulative number of patients with relapse, the Kaplan-Meier (KM) estimate of the percent of patients without relapse and corresponding standard error and two-sided 95% CI will be provided at each yearly time point (1 year = 360 days). Patients with no relapse, patients for whom follow-up ends before a confirmed relapse occurs, and patients who drop out prior to the relapse will all be censored, i.e. the time to event for these patients will be the time in study (from first dose of fingolimod among all studies to last available visit/evaluation date across all panels).

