2.3 Time frames, baseline, and visit windows

This section defines the study and data time frames, baseline, and rules for visit windows.

2.3.1 Database lock for Study part 2

The analyses specified in this document include data from study part 2 with a database lock planned around December 2018/January 2019. All qualified patients will participate until their scheduled visit closest to 30-Jun-2018 (+/- 3 months), which gives time for one follow-up study visit 3-months post last dose of fingolimod, for patients who discontinuing or completing the study after entering part 2 and who do not continue on commercial Gilenya.

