8.1.2 Annualized relapse rates

Annualized relapse rate (ARR) is defined as the *number of relapses* experienced during a specific period of time adjusted to a one-year period. The ‘number of relapses’ can refer to

either the number of *confirmed relapses* or the number of *all relapses* (including both confirmed and unconfirmed relapses).

Confirmation of relapses is not collected in the following studies: CFTY720D2316, CFTY720D2320, CTY720D2399E1, and the long-term follow-up study prior to protocol amendment 4. Therefore, the number of confirmed relapses during this time is not able to be reported. Additionally, confirmed relapses will not be reported for patients from the CFTY720D2324 study since it is a phase IIIb study and confirmation is not collected in the long-term follow-up study for patients coming from previous studies that are not phase II/III. The number of unconfirmed relapses is also not able to be reported for study CTY720D2399E1 since the study does not collect relapse start dates. However, note that the time during which number of relapses is not able to be counted and the time off study for patients who re-enrolled into the long-term follow-up study will still be included in the time in study, which can make the ARR appear lower than it actually is. If confirmation of a relapse is missing or not collected, the relapse will be treated as an unconfirmed relapse. Therefore, ARR based on all relapses (confirmed or unconfirmed) should be considered a more reliable estimation of relapse rate than ARR based on confirmed relapse.

The group level (aggregate) ARR will be calculated as follows: (total number of relapses) / (total number of days in the study for all patients for that specific period of time) x 365.25.

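### Confirmed-relapse rates and time to first confirmed relapse count time in which confirmation was not collected, and the Part 2 SAP adds all of Part 2 without saying so

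*SAP*

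**What the plan says.** Section 8.1.2 of both SAPs lists where confirmation is missing: "Confirmation of relapses is not collected in the following studies: CFTY720D2316, CFTY720D2320, CTY720D2399E1, and the long-term follow-up study prior to protocol amendment 4". It adds that in the long-term study confirmation is not collected for patients whose earlier study was not phase II/III, and that "confirmed relapses will not be reported for patients from the CFTY720D2324 study since it is a phase IIIb study". A relapse without confirmation data is treated as unconfirmed. Time in which relapses cannot be counted, and time off study before re-enrolment, "will still be included in the time in study, which can make the ARR appear lower than it actually is". The SAPs conclude that the all-relapse ARR is the more reliable figure.

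Section 8.1.3 makes no deduction. To end of treatment, "the time in study (days) is calculated as: last dose date of fingolimod" minus the first fingolimod dose date in any study, plus one day. To end of follow-up, it runs to the last visit or evaluation in any data panel.

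Section 8.1.4 plans every relapse analysis twice, for all relapses and for confirmed relapses. The negative binomial offset is the log of this same time. For Kaplan-Meier, "Patients with no relapse, patients for whom follow-up ends before a confirmed relapse occurs" and dropouts are censored at the full time in study. The Part 2 SAP repeats these rules and draws the curve to the end of Part 2.

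The protocol defines confirmed relapse for Part One only (6.4.1) and assesses EDSS only in Part One (6.4.2). In Part Two, relapses are still recorded, for safety monitoring (9.5.1.1).

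**The concern.** A period that cannot produce a confirmed relapse should not count as time at risk of one. Here it counts fully, so confirmed ARR is pulled down and the confirmed-relapse-free percentage is pushed up. Both errors favour the drug. The SAPs' warning covers ARR only, so the Kaplan-Meier tables and plots would be printed with standard errors and 95% intervals and no caveat.

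The Part 2 SAP carries over the Part I list of unascertained periods without adding Part 2. Its full analysis set contains only patients who entered Part 2 (2.5), so the omission reaches essentially everyone analysed.

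Relapse occurrence in Part One is a secondary objective (protocol 2.2).

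**Working it through.** **1. No planned figure to reproduce.** Neither document states an expected ARR or relapse-free percentage. The check applies the SAP formulas to the periods the documents describe.

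**2. ARR.** Group ARR = relapses / days in study x 365.25. If a share u of person-time cannot yield a confirmed relapse but stays in the denominator, then at a constant rate expected ARR = true ARR x (1 - u). The shortfall equals u. As an illustration with an assumed true rate of 0.20 per year, u = 10% prints 0.18 and u = 30% prints 0.14. For Part I, u cannot be computed because no cohort split is given.

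**3. Length of Part 2.** The Part I SAP (2.3.1) says "All qualified patients will have end of study visit scheduled around 31st Oct 2016". The protocol (3.1) ends Part One at about 30-Jun-2016. The Part 2 SAP (2.3.1) says "All qualified patients will participate until their scheduled visit closest to 30-Jun-2018".
- 31-Oct-2016 to 30-Jun-2018 = 607 days; 607/365.25 = 1.66 years.
- 30-Jun-2016 to 30-Jun-2018 = 2.00 years.

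**4. Share of exposure.** Protocol 3.3 gives 7-15 years of exposure.
- 1.66/15 = 0.111 and 1.66/7 = 0.237.
- 2/15 = 0.133 and 2/7 = 0.286.
- Pooled at the mean of an even spread (11 years): 1.66/11 = 0.151 and 2/11 = 0.182.

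Confirmed ARR to end of treatment in the Part 2 report is therefore 11-29% too low per patient, or 15-18% pooled, from Part 2 time alone.

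**5. Kaplan-Meier in the Part 2 report.** Let exposure E be uniform on 7-15 years, with the last L years (1.66 or 2.00) lacking confirmation and a constant true hazard lambda. A patient is recorded as event-free at t with probability exp(-lambda x min(t, E - L)). The hazard the pooled curve estimates is lambda x (event-free with E - L > t) / (event-free with E > t), integrated numerically:

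| lambda per year | S(10)/S(8) as planned | true S(10)/S(8) |
|---|---|---|
| 0.10 | 0.869-0.880 | 0.819 |
| 0.15 | 0.812-0.828 | 0.741 |
| 0.20 | 0.76-0.78 | 0.670 |

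At 0.15 per year, S(10) is 0.261-0.272 against exp(-1.5) = 0.223. The curve flattens but does not go flat, because time runs from first dose and longer-exposed patients are still in Part One at the same exposure time.

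**6. Two cohorts.** For D2324, section 8.1.2 says confirmed relapses are not reported, but not whether those patients and their time leave the confirmed analyses. D2325 is listed as a prior study (Part I SAP, section 1). It is not in the phase II/III list in 2.5.1, "D2201, D2301, D2302, and D2309 before entering the long-term follow-up study part I", so by the general clause its long-term-study time has no confirmation. Section 8.1.2 does not name it, and its core study is not listed as unconfirmed.

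**7. Comparison within the SAP.** Time to EDSS 4/6/7 is censored at the last EDSS assessment (Part I SAP, 8.3.2). Confirmed relapse also depends on EDSS but is not handled that way.

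**The case against.** The ARR handling is a disclosed choice. Both SAPs state the bias and its direction, prefer the all-relapse ARR, and report all-relapse results beside every confirmed analysis. The analyses are secondary and descriptive, with no hypothesis test. This stands and limits the harm, but it does not cover Kaplan-Meier.

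The Part 2 SAP's general rules, under which uncollected confirmation means unconfirmed and uncountable time stays in, reach Part 2 without naming it. They do, and that is how Part 2 time enters the denominator. A reader of the printed list would still not learn that Part 2 has no confirmation.

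The cohort ambiguity is minor. The general clause settles D2325, and the natural reading for D2324 is that its time is kept. That is fair: these points need clarifying and do not carry the finding.

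The figures depend on assumptions. The 7-15 years describes study patients generally, not the Part 2 subset, and every figure concerns Part 2 rather than the Part One objective. Allowing the three-month window around 30-Jun-2018 (about 91 days), Part 2 lasts (607 - 91)/365.25 = 1.41 to (730 + 91)/365.25 = 2.25 years. The share is then 1.41/15 = 9% to 2.25/7 = 32%. With exposure uniform on 10-15 years and a hazard of 0.15, 10-year relapse-free is 23-24% against 22%. These points are correct. They change the size, not the direction.

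Protocol 6.1 collects relapse history for any gap between the previous study and this one, so some gap time may be ascertained for all relapses. This stands, and the fix allows for it.

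**Conclusion.** The concern holds. Followed exactly, the plan gives a confirmed ARR that is too low and a confirmed-relapse-free percentage that is too high. Only the ARR bias is disclosed, and the Part 2 SAP adds Part 2 time without listing it as unascertained.

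The 11-29% ARR shortfall applies to a patient who stays through Part 2, has confirmation throughout the earlier period and relapses at a constant rate. Early leavers contribute less Part 2 time. The 26-27% against 22% at year 10 also assumes exposure spread evenly over 7-15 years and a hazard of 0.15 per year; it shrinks if Part 2 patients have longer exposure. No size is claimed for Part I. This should be fixed, but it does not affect the primary safety objective.

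**What to change.** 1. **Both SAPs, confirmed ARR.** Limit the count, denominator and offset to patients and periods in which confirmation was collected, using the Amendment 4 approval and re-enrolment dates already recorded (protocol 6.2). State that D2324 patients and their time are excluded, and that D2325 patients' time in the long-term study is excluded.
2. **Confirmed-relapse Kaplan-Meier.** Exclude patients for whom confirmation was never collected and end follow-up no later than the end of Part One. For phase II/III patients with a gap before Amendment 4, add a curve censored at the gap as a sensitivity analysis, with a printed caveat and numbers at risk.
3. **Part 2 SAP.** Name Part 2 as unascertained, drop confirmed-relapse analyses of Part 2 time and keep the all-relapse analyses.
4. **All relapses.** Remove D2399E1 time and re-enrolment gaps from the denominator and offset where no relapse data were collected.

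The cost is SAP wording and one derived-time variable. There will be fewer person-years and a less favourable confirmed ARR.

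Gap censoring stays a sensitivity analysis because about 3,750 of about 4,150 patients (3,750/4,150 = 90%, all phases; Amendment 5 and 11 rationales) had enrolled by February 2012. As the main analysis it could remove most long-term-study follow-up. The main curve therefore keeps some overstatement from that gap and does not use the same time base as the corrected ARR. The caveat must say both.

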8.1.3 Time in study

For the analysis of ARR from first dose of fingolimod to end of study treatment, the time in study (days) is calculated as: last dose date of fingolimod – first dose date of fingolimod among all studies + 1 day. Similarly, the time in study from first dose of fingolimod among all studies to end of follow-up is calculated as: last available visit/evaluation date across all panels – first dose date of fingolimod among all studies + 1 day.

For the analysis of ARR from first dose of fingolimod among all studies to end of a particular month (i.e. “Month 6”, “Month 12”, “Month 24”, and every 12 months from then on), “Month 0 to X” time in study will be calculated as minimum of (first dose date of fingolimod + integerpart(X/12*365.25) where X denotes the month, last available visit/evaluation date across all panels) – first dose date of fingolimod + 1 day.

8.1.4 MS relapses analyses

MS relapses analyses will be conducted on the fingolimod full analysis set. All analyses will be done for all relapses (confirmed and unconfirmed) and for confirmed relapses.

A summary of ARRs will be presented by time period (cumulative time intervals: ‘Month 0 to Month 6’, ‘Month 0 to Month 12’, ‘Month 0 to Month 24’, ‘Month 0 to Month 36’, ... incremented by 1 year for each successive interval, plus ‘Month 0 to end of study treatment’ and ‘Month 0 to end of follow-up’) from first dose of fingolimod among all studies. The summary will include number of patients summarized, number of relapses, time in study (days), and group level ARR. In addition, model based estimates of ARR and corresponding two-sided 95% confidence interval will be obtained by fitting a negative binomial regression model adjusted for the number of relapses in the last two years prior to

enrolment in the core study and EDSS score at first dose of fingolimod baseline, with the logarithm of the time in study as the offset variable.

A summary of relapse characteristics will be displayed by time period (consecutive yearly intervals: 'Month 0 to Month 12', 'Month 12 to Month 24', etc., plus 'End of study treatment to End of follow-up') from first dose of fingolimod among all studies. Relapse characteristics will be summarized at a patient level (the number and percent of patients with at least one relapse type) and at a relapse event level (the number and percent of a particular type of relapse out of the total number of relapses). The types of relapses being summarized include: relapses which affect daily activities, relapses which require steroids, and relapses which require hospitalization.

The time to first onset of relapse from first dose date of fingolimod among all studies will be analysed. Specifically, the number of patients at risk, the cumulative number of patients with relapse, the Kaplan-Meier (KM) estimate of the percent of patients without relapse and corresponding standard error and two-sided 95% CI will be provided at each yearly time point (1 year = 360 days). Patients with no relapse, patients for whom follow-up ends before a confirmed relapse occurs, and patients who drop out prior to the relapse will all be censored, i.e. the time to event for these patients will be the time in study (from first dose of fingolimod among all studies to last available visit/evaluation date across all panels).

A Kaplan-Meier plot of time to first relapse from first dose of fingolimod to end of the long-term follow-up study part I will be presented.

8.2 Analysis of MRI

MRIs are required only for patients from phase II/III trials who had MRI assessments in prior fingolimod trials. MRI parameters analyzed in this study include: number of new/newly enlarging T2 lesions, volume of T2 lesions, T1 hypointense (black hole) volume, percent brain volume change, and annualized rate of brain volume change. MRI data will be analyzed for the fingolimod full analysis set.

8.2.1 Annualized rates of new-/newly enlarging T2 lesions

Annualized rate of new/newly enlarging T2 lesions is defined as the *number of new or newly enlarging T2 lesions* experienced during a specific period of time adjusted to a one-year period. The group level annualized rate of new/newly enlarging T2 lesions will be calculated as follows: (total number of new/newly enlarging T2 lesions) / (total number of days in the study for all patients for that specific period of time) x 365.25. The number of days in study will be calculated based on MRI scan date and first dose date of fingolimod. The annualized rate will be provided from first dose of fingolimod.

In addition to a group level annualized rate estimate, another annualized rate estimate and corresponding two-sided 95% confidence interval will be presented from a negative binomial (NB) regression model adjusted for total volume of T2 lesions at first dose of fingolimod baseline. Log (time in study) will be the offset variable.

These annualized rate summaries will be presented by cumulative yearly intervals: Month 0 to Month 3, Month 0 to Month 6, Month 0 to Month 12, Month 0 to Month 24, etc.

In general the number of new/newly enlarging T2 lesions is provided by the reading center. It is obtained by comparing two scans (e.g. the baseline scan to the Month 24 scan). If an assessment is provided by the reading center, then this should be used. Derived parameters should only be used when no assessment from the reading center is available. It is of note that any such derived number is an approximation. When an assessment is not provided by the reading center (i.e. 2399 results relative to FDF), derivation rules regarding number of new/newly enlarging T2 lesions relative to FDF baseline should be followed as below:

- Patients who were randomized to fingolimod in core: new/newly enlarging T2 lesions relative to FDF baseline = new/newly enlarging T2 lesions relative to core baseline.
- Patients who were randomized to another treatment (placebo or interferon) than fingolimod in core and switched to fingolimod in extension:
 - If the record of extension FDD was available in the extension database, new/newly enlarging T2 lesions relative to FDF baseline = new/newly enlarging T2 lesions relative to extension FDD.
 - If no records relative to extension FDD were available, new/newly enlarging T2 lesions relative to FDF baseline = max(result relative to FDD – end of core result relative to FDD, 0).

